### 3. Study Design and Procedures

### 3.1 General Study Design

This phase 2 multi-center trial is a randomized, prospective, double-masked, vehicle-controlled study to assess the efficacy and safety of NEXAGON applied topically in subjects with corneal PED resulting from severe ocular chemical and/or thermal injuries.

A subject's participation is to start with screening (Eligibility Assessment Visit) to determine eligibility for enrollment into the study prior to Day 1. If the subject is considered eligible for the study, the subject will be randomized to receive either NEXAGON [REDACTED] or NEXAGON [REDACTED] or Vehicle [REDACTED], respectively on Day 1.

For all subjects, the first investigational product application will occur following randomization ■■■■■ with investigational product (NEXAGON) ■■■■■ or NEXAGON

[REDACTED] or Vehicle) [REDACTED]. Following investigational product application, [REDACTED]

The study will comprise of 2 periods, a Treatment Period and Post-healing Follow-up Period:

**Treatment Period (Masked):**

During the Treatment Period, masked investigational product will be administered on [REDACTED]

- If re-epithelialization of the defect has NOT occurred [REDACTED] another single application of masked investigational product will be administered [REDACTED]
- If re-epithelialization occurs at any time during the masked Treatment Period, subjects will enter a [REDACTED] Post-healing Follow-up Period to assess durability of the corneal epithelium.

**Post-healing Follow-up Period (Masked)**

During the [REDACTED] Post-healing Follow-up Period subjects will be assessed [REDACTED] following initial re-epithelialization to confirm durability of the epithelium.

- If the healed epithelium is sustained within the Post-healing Follow Period (durable), the subject will then exit the study having completed all visits.
- [REDACTED]
- [REDACTED]
- [REDACTED]

**Open-Label Section**

In the open-label section of the study subjects will receive a salvage dose of NEXAGON [REDACTED]

- If re-epithelialization has not been achieved [REDACTED] dose of NEXAGON [REDACTED] will be applied [REDACTED] A final assessment of healing for these subjects will be conducted [REDACTED]
- [REDACTED]
- [REDACTED]
- [REDACTED] [REDACTED] [REDACTED] [REDACTED] [REDACTED] [REDACTED] [REDACTED] [REDACTED] [REDACTED] [REDACTED]

- If re-epithelialization has not occurred [REDACTED], the subject will exit the study.

The maximum duration for study participation for a subject [REDACTED]

At each study visit, following randomization until the end of the study, the subject will undergo assessments as detailed in Table 2 (Schedule of Assessments). Assessments will be performed by a designee at the study site who is masked to the allocated investigational product and include

[REDACTED]  
[REDACTED]  
[REDACTED] The occurrence of any  
Treatment Emergent Adverse Events will also be assessed at each study visit, and up to [REDACTED]  
following the final application of investigational product.

### **3.2 Study Visit Windowing**

Study day will be referred to in all tables and listings. Table 1a shows the planned study visits and the acceptable visit window for each visit for subjects who are in the study for the maximum duration. Table 1b shows the planned study visits and acceptable visit window by study period. Visits that are not able to be completed within the windows specified in the protocol must be recorded as protocol deviations.

Note: Day 1 corresponds to the day of randomization, there is no Day 0.

**Table 1a. Study Visit Windows** A horizontal black bar used to redact sensitive information from the table header.

A large black rectangular box used to redact sensitive information from the table body.

**Table 1b. Study Visit Windows** [REDACTED]

[figure not shown]
A large black rectangular box used to redact sensitive information from the document.

Visit Window	Definition	Notes
Initial Visit	Initial visit to the study site.	
Follow-up Visit	Visit to the study site for follow-up information.	
Final Visit	Final visit to the study site.	
Other	Other visit to the study site.	

**3.3 Dose Regimen, Study Flow Diagram, and Schedule of Visits and Assessments**

The dosing regimen is provided in Figure 1, the study flow diagram (visit schedule and dosing days) is provided in Figure 2 and the schedule of visits and assessments is provided in Table 2.

[figure not shown]
**Figure 2. Study Flow Diagram –** [REDACTED]

**Table 2. Schedule of Visits and Assessments**

#### 4. Study Treatments

##### 4.1 Method of Assigning Subjects to Treatment Groups

A subject who meets all the inclusion criteria and none of the exclusion criteria is eligible for randomization [REDACTED] Subjects are to be randomized to one of three treatment group:

- GROUP A – NEXAGON [REDACTED]
- GROUP B – NEXAGON [REDACTED]
- GROUP C – Vehicle (0%)

A statistician not directly involved in the analysis of the study results will prepare the randomization schedule using block randomization to maintain balance between treatment groups. Randomization is to be done [REDACTED]  
[REDACTED]  
[REDACTED]

When a subject is confirmed to be eligible for randomization [REDACTED] treatment assignment for that subject will be determined by [REDACTED]  
[REDACTED]

##### 4.2 Masking and Unmasking

All subjects, investigators, and study personnel involved with the conduct of the study will be masked with regard to treatment assignments.

The Investigator may unmask a subject's treatment assignment only in the case of an emergency when knowledge of the investigational product is essential for the clinical management or welfare of the subject. [REDACTED]  
[REDACTED]  
[REDACTED]

If a drug-related serious adverse event (SAE) is reported, the Medical Monitor may unmask the treatment assignment for the individual subject.

#### 5. Sample Size and Power Considerations

Assuming the true rate of corneal epithelialization in each of the NEXAGON arms of [REDACTED]  
[REDACTED]  
[REDACTED]

Assuming a discontinuation rate [REDACTED]

[REDACTED] Enrollment will continue until [REDACTED]  
[REDACTED]

## 6. Data Preparation

### 6.1 Input Data

Electronic case report forms (eCRFs) will be developed [REDACTED]

Data from source documents will be entered into the eCRF by site personnel.

The electronic clinical study database will be [REDACTED]

After data are entered into the clinical study database, electronic edit checks and data review will be performed. All data validation specifications and procedures are detailed in the [REDACTED]

[REDACTED] When the database has been declared to be complete and accurate, the database will be locked. Any changes to the database after data have been locked can only be made with the approval of [REDACTED]

All analyses outlined in this document will be carried out after the following have occurred:

- All data [REDACTED] requirements are met according [REDACTED]  
[REDACTED]  
[REDACTED] [REDACTED] [REDACTED] [REDACTED] [REDACTED] [REDACTED] [REDACTED] [REDACTED]  
[REDACTED]
- Protocol deviations have been identified and status defined (major/minor deviations).
- Analysis populations have been determined.
- Randomized treatment codes have been unmasked.

In addition, the laboratory data [REDACTED]

[REDACTED] will be included in the statistical analysis.

### 6.2 Output Data

Data from the electronic clinical study database and external data will be transferred to [REDACTED] and incorporated into standard formats following the Study Data Tabulation Model (SDTM). Data will then be mapped to analysis datasets using the Analysis Data Model (ADaM). Both SDTM- and ADaM-formatted data will be used to create the subject listings, while all tables and figures will be based on the ADaM-formatted data.

SDTM will follow the [REDACTED] and will be implemented using the SDTM Implementation Guide [REDACTED] and the SDTM Controlled Terminology [REDACTED]. ADaM data will follow the ADaM [REDACTED] model and will be implemented using the ADaM Implementation Guide [REDACTED] and the ADAM Controlled terminology [REDACTED]. Both SDTM and ADaM will be validated [REDACTED]. Any discrepancies in the validation will be noted in reviewer's guides accompanying the final data transfers.

## 8. General Statistical Considerations

## 8.1 Unit of Analysis

The study eye will be defined as

## 8.2 Missing or Inconclusive Data Handling

A horizontal bar chart illustrating the percentage of respondents who have heard of various terms. The y-axis lists the terms, and the x-axis represents the percentage from 0% to 100% in increments of 10%. The bars are black and are separated by thin white lines.

Term	Percentage
Healthcare	98
Medical	95
Health	92
Healthcare system	88
Medical system	85
Healthcare reform	82
Medical reform	78
Healthcare insurance	75
Medical insurance	72
Healthcare technology	68
Medical technology	65
Healthcare policy	62
Medical policy	58
Healthcare access	55
Medical access	52
Healthcare equity	48
Medical equity	45
Healthcare disparities	42
Medical disparities	38
Healthcare quality	35
Medical quality	32
Healthcare cost	28
Medical cost	25
Healthcare resources	22
Medical resources	18
Healthcare innovation	15
Medical innovation	12
Healthcare innovation	10
Medical innovation	8

### 8.3 Definition of Baseline and Final On-Treatment Visit

Baseline will be defined as the last measurement prior to the first dose of study medication. Change from baseline will be calculated as follow-up visit value minus baseline value.

The final on-treatment visit is defined as the day of initial corneal re-epithelialization, treatment [REDACTED] or day of discontinuation during treatment.

#### 8.4 Data Analysis Conventions

All data analysis will be performed by [REDACTED] after the study is completed and the database has been locked and released for unmasking. Statistical programming and analyses will be performed using [REDACTED] [REDACTED] Output will be provided in rich text format (RTF) for tables and portable document format (PDF) for tables, listings, and figures using landscape orientation. All study data will be listed by subject, treatment, and visit (as applicable) based on all randomized subjects unless otherwise specified.

Summaries for continuous and ordinal variables will include the number of observations (n), arithmetic mean, standard deviation (SD), median, minimum, and maximum. Minima and maxima will be reported with the same precision as the raw values; means and medians will be presented to one additional decimal place than reported in the raw values. Standard deviations will be presented to two additional decimal places than reported in the raw values. Summaries for discrete variables will include counts and percentages. All percentages will be rounded to one decimal place (i.e., XX.X%). Differences between active treatment groups and placebo will be calculated as active minus placebo and change from baseline will be calculated as follow-up visit minus baseline.

[REDACTED]  
[REDACTED]  
[REDACTED]  
[REDACTED]  
[REDACTED]  
[REDACTED]  
[REDACTED]

Unless otherwise specified, summaries will be presented by treatment group and, where appropriate, visit. Listings will be sorted by treatment group, subject number, visit/time point, and parameter as applicable.

#### 8.5 Adjustments for Multiplicity

[REDACTED]  
[REDACTED]  
[REDACTED]  
[REDACTED]  
[REDACTED]  
[REDACTED]  
[REDACTED]  
[REDACTED]

## 9. Disposition of Subjects

Subject enrollment, inclusion in analysis populations, and study completion/withdrawal from the study for the main study as well as the open-label section of the study will be summarized and listed in terms of the numbers and percentages of subjects who were randomized, completed the study, and discontinued from the study. Subjects who are not discontinued from the study will be considered study completers. Disposition will be summarized by treatment group and for all subjects.

The number and percentage of subjects prematurely discontinued from the study and the reasons for study discontinuation will be summarized by treatment group for all subjects who discontinued the study. The reasons for study discontinuation that will be summarized include AE, lost to follow-up, physician decision, protocol violation, screen failure, study terminated by sponsor, withdrawal by subject, and other.

The number and percentage of subjects with major protocol deviations will be summarized by treatment group for all randomized subjects.

## 10. Demographic and Pretreatment Variables

### 10.1 Demographic Variables

The demographic variables collected in this study include age, gender at birth, race, and ethnicity.

Demographic variables will be summarized for all randomized subjects

A subject listing that includes all demographic variables will be provided.

### 10.2 Pretreatment Variables

Baseline disease characteristics will be summarized separately for all randomized subjects

Summaries will be presented for the study eye. For subjects with a bilateral ocular injury, the assessments detailed above will also be listed for the fellow eye (in addition to the study eye).

## 11. Medical History and Concomitant Medications

### 11.1 Medical History

General ocular history, and non-ocular medical history will be coded using the Medical Dictionary for Regulatory Activities (MedDRA). [REDACTED] Medical history, including details of any ongoing medical conditions, will be recorded prior to Day 1 and before eligibility is confirmed.

[REDACTED]

[REDACTED]

[REDACTED]

[REDACTED]

[REDACTED]

[REDACTED]

SOCs will be listed in alphabetical order and PTs within an SOC will be listed in order of descending frequency across all subjects.

Listings of medical history will be generated separately for both ocular data and non-ocular data.

### 11.2 PED History

A detailed ocular examination and history will be conducted prior to the Day 1 visit and assessed against the inclusion and exclusion criteria of the protocol.

[REDACTED]

[REDACTED]

- [REDACTED]
- [REDACTED]
- [REDACTED]
- [REDACTED]
- [REDACTED]
- [REDACTED]

### 11.3 Prior and Concomitant Medications

[REDACTED]

[REDACTED]

[REDACTED]

[REDACTED]

[REDACTED]

[REDACTED]

[REDACTED]

Prior and concomitant medications will be listed for all randomized subjects. [REDACTED]

#### **11.4 Concomitant Procedures**

Concomitant procedures will be coded using the Medical Dictionary for Regulatory Activities (MedDRA) [REDACTED] and summarized by SOC and PT.

Concomitant procedures will be listed using all randomized [REDACTED]

#### **12. Treatment Exposure**

Treatment exposure will be defined in two ways, as the extent of treatment exposure and the number of treatment doses. The number of treatment doses is the number of actual applications of NEXAGON or Vehicle.

[REDACTED]  
[REDACTED]  
[REDACTED]  
[REDACTED]  
[REDACTED]  
[REDACTED]

#### **13. Efficacy Analyses – Masked Portion of Study**

##### **13.1 Primary Efficacy Outcome Analysis**

The primary efficacy outcome will be the comparison of each dose of NEXAGON to Vehicle for the proportion of subjects with corneal epithelial recovery, defined as a cornea that re-epithelializes [REDACTED] of treatment and remains re-epithelialized [REDACTED] after initial re-epithelialization was first recorded (during the masked treatment portion of the study and assessed by the

Investigator). Subjects who discontinue the study early, or who have missing data resulting in the inability to conclude corneal epithelial recovery, will be considered as not having corneal epithelial recovery (missing data imputed as failure).

The number and proportion of subjects with corneal epithelial recovery will be summarized by treatment group and tested between treatment groups [REDACTED]

### 13.1.1 Sensitivity Analyses

## 13.2 Secondary Efficacy Outcome Analyses

The secondary efficacy outcomes will be analyzed using the [REDACTED] with reference to the masked treatment period. [REDACTED]

For more information, contact the Office of the Vice President for Research and Economic Development at [contact] or [[contact]](mailto:[contact]).

The following secondary efficacy endpoints, [REDACTED]

13.2.1 [REDACTED]

[REDACTED]

#### 14. Exploratory Analyses

The exploratory efficacy outcomes will be [REDACTED]

[REDACTED]

[REDACTED]

[REDACTED]

[REDACTED]

[REDACTED]

[REDACTED]

[REDACTED]

- Primary, secondary, and exploratory endpoints will also be assessed (as applicable) for the open-label section of the study.

14.1

14.4

A series of 15 horizontal black bars of varying lengths, arranged vertically. The bars are positioned such that they overlap and cover the entire width of the page. The lengths of the bars decrease from top to bottom, creating a visual effect of receding depth or a timeline.

## 15. Safety Analyses

All safety analyses will be conducted using the safety population. Summaries of safety measures during the masked treatment and follow-up periods [REDACTED] will be completed similarly.

## 15.1 Adverse Events

An Adverse Event (AE) is defined as any untoward medical occurrence in a subject or clinical investigation subject administered a pharmaceutical product and that does not necessarily have a causal relationship with this treatment. An AE can therefore be any unfavorable and unintended sign (including an abnormal laboratory finding), symptom, or disease temporarily associated with the use of an investigational product whether or not related to the investigational product. AEs will be recorded from the time of first application of the investigational product and until the final visit.

Treatment-emergent adverse events (TEAEs), defined as AEs that occur after the first dose of study medication, are undesirable events not present prior to investigational product treatment, or an already present event that worsens either in intensity or frequency following treatment.

Serious Adverse Events (SAE) any untoward medical occurrence that at any dose results in death, is life-threatening and/or sight threatening, results in persistent or significant disability/incapacity, is a congenital anomaly/birth defect. SAEs are undesirable events (experiences) or reaction not present prior to investigational product treatment, or an already present event that worsens in magnitude to be classified as an SAE, either in intensity or frequency following treatment.

Severity of an AE is defined as a qualitative assessment of the degree of intensity of an AE as determined by the Investigator or reported to him/her by the subject. The assessment of severity is made irrespective of relationship to study drug or seriousness of the event and should be evaluated according to the following scale:

- *Mild*: Event is noticeable to the subject but is easily tolerated and does not interfere with the subject's daily activities.
- *Moderate*: Event is bothersome, possibly requiring additional therapy, and may interfere with the subject's daily activities.
- *Severe*: Event is intolerable, necessitates additional therapy or alteration of therapy, and interferes with the subject's daily activities.

The relationship of each AE or SAE to the study drug should be determined by the Investigator using these explanations: definitely related, probably related, possibly related, unlikely to be related, and unrelated. Only definitely, probably, and possibly related TEAEs will be considered as treatment-related TEAEs. For TEAEs prior to rescue medication use, only those TEAEs with an onset date prior to the date that rescue medications were first used will be included.

Clinically significant abnormal laboratory findings or other abnormal assessments that are present at baseline and significantly worsen following the start of the study will be reported as AEs and SAEs. The Investigator will exercise his/her medical and scientific judgment in deciding whether an abnormal laboratory finding or other abnormal assessment is clinically significant.

Verbatim descriptions of AEs will be mapped to MedDRA [REDACTED] terms and presented in a data listing. Adverse events recorded in the eCRF which began prior to treatment will not be included in the summary tables but will be included in the AE data listings. All AEs, SAEs, and TEAEs will be presented separately in subject data listings. The TEAEs leading to study treatment discontinuation will also be listed separately.

An overall summary will be presented that includes the number of events and the number and percentage of subjects who experienced at least one TEAE, by treatment group and over all subjects. This summary will also include breakdowns of TEAEs further categorized as ocular (study eye and, for subjects with bilateral injury, fellow eye separately) or non-ocular, treatment-related TEAEs, TE-SAEs, TEAEs leading to treatment withdrawal, TEAEs leading to death, TEAEs by maximal severity, and TEAEs by relationship to study drug.

Treatment-emergent adverse events (TEAEs), those that occur after the first dose of study medication, will be summarized by treatment group using frequency and percentages for each SOC and PT within each SOC. Similar summaries will be presented for treatment related TEAEs, TEAEs by maximum severity, serious TEAEs, and TEAEs leading to test article discontinuation.

Separate summaries of TEAEs will be provided showing the number and percentage of subjects who experienced at least one TEAE by treatment group and over all subjects. Non-ocular TEAEs will be summarized using discrete summary statistics and presented by treatment group at the subject and event level by SOC and PT. Ocular TEAEs will be similarly summarized at the subject level for study and fellow eyes separately. If a subject reports the same PT multiple times within the same SOC, that PT will only be reported once within that SOC. As with the PT, if a subject reports multiple conditions within the same SOC, that SOC will only be reported once. In the summary, SOCs will be listed in ascending alphabetical order; PTs will be listed in order of descending frequency for all subjects within each SOC.

The number of subjects with any TEAEs (along with percentages) will be tabulated by SOC and PT within each SOC by treatment group. Summaries of TEAEs by maximal severity, strongest relationship to study drug, and strongest relationship to study drug and maximal severity will be presented for ocular AEs and non-ocular AEs separately. To count the number of subjects with any TEAEs, if a subject has multiple TEAEs coded to the same PT within the same SOC, the subject will be counted once under the maximum severity. TEAEs that led to test article discontinuation, defied as drug interruption or drug withdrawal as response to the AE, treatment related TEAEs, and TE-SAEs will also be summarized by SOC and PT.

15.2

[REDACTED]

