5.2. Inclusion Criteria

A subject will be eligible for inclusion in this study only if ALL of the following criteria apply:

1. Male and female of any age.
2. Clinically non-infected, corneal persistent epithelial defect (PED) as a result of a severe chemical and/or thermal ocular injury in one or both eyes.
3. [REDACTED]
4. [REDACTED]
5. Providing written informed consent and ability to comply with the visit and dosing schedule.

NOTES:

- [REDACTED]
- [REDACTED]
- [REDACTED]
- [REDACTED]

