6.7.4. Slit Lamp Examination

Slit lamp biomicroscopy (without pupil dilation) will be performed during the study on both the study eye treated with investigational product and fellow eye. Observations for the slit lamp biomicroscopy will be graded as detailed in [Appendix 5](#).

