6.7.8. Intraocular Pressure

Intraocular pressure (IOP) will be assessed in both the study eye and fellow eye only on the days shown in [Table 1](#): Schedule of Assessments.

[REDACTED]
[REDACTED]
[REDACTED]

A final IOP measurement will be taken when the subject exits the study.

The method used to measure IOP, whilst not standardized across study sites, MUST be kept the same for each individual subject within a study site.

[REDACTED]

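### The overall TEAE summary limits its fellow-eye line to bilateral injury, so a fellow-eye event in a unilaterally injured subject has no row in the ocular/non-ocular breakdown, contrary to the eye-level summary later in the same section

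*SAP*

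**What the plan says.** SAP 15.1 opens the overall summary (Table 14.3.1 in the SAP's list of tables for the final analysis) with a line giving "the number of events and the number and percentage of subjects who experienced at least one TEAE", by treatment group and overall. That line has no restriction by eye or by laterality of injury. The same summary then breaks TEAEs down as "categorized as ocular (study eye and, for subjects with bilateral injury, fellow eye separately) or non-ocular". Its remaining breakdowns (treatment-related, serious, leading to withdrawal, leading to death, by severity, by relationship) carry no eye restriction.

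Later in SAP 15.1 the rule for the system organ class and preferred term summaries is different: "Ocular TEAEs will be similarly summarized at the subject level for study and fellow eyes separately". Summaries by severity and relationship "will be presented for ocular AEs and non-ocular AEs separately", again without reference to laterality. For listings, "All AEs, SAEs, and TEAEs will be presented separately in subject data listings".

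The protocol admits subjects with "severe chemical and/or thermal ocular injury in one or both eyes" (Section 5.2), so an uninjured fellow eye is possible. Both eyes are examined for safety whatever the laterality. Slit lamp examination is "performed during the study on both the study eye treated with investigational product and fellow eye" (Section 6.7.4), and "Intraocular pressure (IOP) will be assessed in both the study eye and fellow eye" on scheduled days (Section 6.7.8).

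**The concern.** A breakdown placed under a total is normally expected to be exhaustive. Here the fellow-eye group is conditional on bilateral injury, and no other ocular group is named to receive fellow-eye events from the remaining subjects. Two things follow if a programmer takes the sentence at its word. The event counts in the breakdown may not reconcile with the line above them. The fellow-eye line in the headline table may also not match the fellow-eye summary by system organ class and preferred term, because the two cover different subjects.

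The events concerned are of some interest. When only one eye was injured, an event in the other eye is harder to put down to the original injury than an event in the study eye. Their number may be small or nil, but they should have a defined place in the table.

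**Working it through.** The plan gives no figure on this point, so the check is an accounting of categories.

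**Step 1. Define the groups.** Assume each TEAE is recorded either against one eye or as non-ocular. Let

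- S = study-eye TEAEs, all subjects;
- FB = fellow-eye TEAEs in bilaterally injured subjects;
- FU = fellow-eye TEAEs in unilaterally injured subjects;
- N = non-ocular TEAEs.

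**Step 2. Can FU be non-zero?** Yes. Protocol 5.2 admits injury to one eye. The adverse event definition in Protocol 9.1 and SAP 15.1 is not limited to an eye. Slit lamp and pressure measurements cover the fellow eye with no bilateral condition. Where the protocol wants that condition it writes it: Appendices 2, 3 and 8 (symptoms, pain, physician assessment) add the fellow eye only in bilateral injury.

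**Step 3. Compare the lines of the overall summary, read literally.**

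- All-TEAE line, events: S + FB + FU + N.
- Ocular/non-ocular breakdown, events: S + FB + N.
- Difference: (S + FB + FU + N) − (S + FB + N) = FU.

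The difference is zero if no unilaterally injured subject has a fellow-eye TEAE, and otherwise equals the number of such events. This applies to event counts only. Subject counts in such a breakdown need not sum to the total in any case, since one subject can have events in several groups.

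**Step 4. Compare with the later eye-level summary.** Its fellow-eye part has no laterality condition, so it draws on FB and FU together, while the overall summary's fellow-eye line draws on FB alone. The two agree only when FU contributes nothing.

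**Step 5. Does the later summary fill the gap?** In part. It shows the subjects concerned, but ocular TEAEs are planned there at subject level only, whereas non-ocular TEAEs are planned at both subject and event level. In the legible text, the overall summary is the only one that plans event counts together with a split by eye.

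**Step 6. Size.** The documents give neither the proportion of subjects with unilateral injury nor a fellow-eye event rate. FU cannot be estimated, and no percentage is offered.

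**The case against.** The strongest reply is that the parenthesis need not define an exhaustive list. It can be read as saying that ocular is one category and that the fellow eye earns its own line when it too was injured, with any other ocular event staying in a general ocular line. On that reading nothing is missing. Table shells are not in the public documents, and the visible table list jumps from 14.3.2.1 (study eye) to 14.3.6, so the layout cannot be checked and the absence of a fellow-eye table cannot be inferred. The bilateral condition also has precedent: SAP 10.2 and several protocol appendices add the fellow eye only when it was injured.

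A reader might also infer more than the text supports, in two ways. The first is that these events drop out of safety reporting. They do not: they count in the all-TEAE line, in whichever of the table's other lines apply (related, serious, withdrawal, death, severity, relationship), in the later fellow-eye and ocular summaries, and in the listings. The second is that the plan understates the ocular event count. The SAP defines no pooled ocular count for this summary, so there is no stated total to be too low.

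What stands of the reply is that the effect is confined to one breakdown in one table. It does not remove the point. The SAP names no general ocular line, so the benign reading has to be supplied by the programmer, and two programmers could build different tables from the sentence. The precedents concern a baseline listing and injury-related assessments, not the safety examinations, which cover both eyes without condition.

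**Conclusion.** The point holds as an inconsistency within SAP 15.1. As written, the ocular/non-ocular breakdown of the overall TEAE summary has no row for fellow-eye TEAEs in unilaterally injured subjects, and its fellow-eye rule differs from that of the later eye-level summary. The consequence is a shortfall of FU events against the all-TEAE line, possibly zero. It rests on the literal reading of the parenthesis and on such events occurring. It touches neither the collection of safety data nor the efficacy analysis. It is a minor item, justified by its low cost and by the prominence of the table.

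**What to change.** In the overall-summary paragraph of SAP 15.1, replace the parenthetical definition so that the category reads *ocular (study eye and fellow eye separately, all subjects)*. If the sponsor wants to keep the distinction by injury, the fellow-eye row can also be shown by unilateral and bilateral injury, as sub-rows under the all-subjects row. The breakdown is then exhaustive for event counts and follows the same rule as the later eye-level summary.

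The cost is a few words in the SAP and one table shell (Table 14.3.1), with no new data and no change to any other analysis. It is best done before unmasking.
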